### 25 Background and rationale

- 26 Gout is the only form of arthritis that can potentially be "cured" with freedom from recurrent flares
- and disease progression provided long-term treat-to-target urate-lowering therapy (T2T-ULT) is prescribed and adhered with [1]. The goal of T2T-ULT is to achieve and maintain a serum urate
- 29 treatment target of <360 micromol/l [1].
- 30 The T2T strategy is a strategy that defines a treatment and applies tight control (for example, 31 monthly visits and respective treatment adjustments) to reach and maintain this target.
- 32 However, only a suboptimal proportion (around 40%) of patients with gout who start ULT will 33 achieve the serum urate treatment target within 12 months after ULT initiation [2]. Although not
- 34 recommended by international scientific societies, the fire-and-forget (FAF) approach is still widely
- 35 adopted by physicians treating gout patients. It mainly consists of prescribing treatment (e.g., ULT)
- 36 without further dose adjustment based on markers of its effectiveness (e.g., serum urate levels) [3].
- 37 Gout has traditionally been conceptualised as an intermittent inflammatory joint disease. However,
- 38 articular and systemic inflammation during the inter-critical period (i.e. between gout flares) has
- 39 been described recently [4]. Of greater concern, recent publications have demonstrated that flares
- 40 are temporally associated with subsequent cardiovascular events and death due to cardiovascular
- 41 events in the following 30-60 days [5,6]. As T2T-ULT is effective in preventing gout flares after the

42 first year of treatment, long-term T2T-ULT may prevent cardiovascular events and cardiovascular

- 43 mortality by reducing the number of flares [1].
- 44 There is, however, considerable controversy over whether T2T-ULT reduces the risk of adverse 45 cardiovascular events in people with gout, despite the potential for such an effect. Two systematic
- 46 literature reviews showed conflicting results, however, demonstrated several limitations in the
- 47 existing studies' ability to estimate effects on cardiovascular outcomes [7,8]. Firstly, included clinical
- 48 trials that recruited gout patients were underpowered and relatively short (<52 weeks) [7,8].
- 49 Secondly, observational studies that evaluated the association between ULT and cardiovascular
- 50 mortality compared people prescribed ULT with ULT non-initiators so confounding by indication and

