### 188 Statistical analysis

- 189 All descriptive statistics will be reported as number (percentage), mean (standard deviation (SD), or
- 190 median (interquartile range (IQR)) as appropriate.
- 191 Although cloning allows us to account for observed confounding at baseline, the artificial censoring 192 introduced is usually informative [12]. The proposed approach to address this problem is to use 193 inverse probability of censoring weighting. The purpose of the weights is to up-weight patients 194 remaining adherent to the protocol so that they represent censored patients, and as such, maintain 195 the comparability of the study arms throughout the grace period. Survival curves will be estimated 196 using a non-parametric Kaplan-Meier estimator weighted for the inverse probability of censoring 197 weights. The 95% confidence intervals for the difference in 5-year survival and the difference in 198 restricted mean survival times will be obtained using a non-parametric bootstrap with 1000 199 replicates [29].
- 200 First, data from Sweden and the UK will be analysed separately. Then, results will be meta-analysed.
- 201 All analyses will be performed using Stata, version 18 (StataCorp, Texas, USA).

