Ves, N: no.	Y	Y

211

212 Model 1 will be used to meta-analyse the results from CPRD and VEGA datasets. Model 2 will be

213 used to test the internal validity of the association between exposure and outcome and to check

whether the variables available only in CPRD could represent major confounders.

215 Missing data

216 BMI, smoking status, alcohol intake status, and socioeconomic deprivation can have missing data in

217 CPRD. The pattern of missingness will be compared and missingness at random assumed. Missing

- 218 data will be imputed using chained equations. BMI, smoking status, alcohol intake status, and
- 219 socioeconomic deprivation will be modelled using multinomial logistic regression.
- 220 Subgroup analyses
- 221 We will perform some sensitivity analyses to test the robustness of the association between the 222 exposure and the outcome.
- We will consider a SU target of ≤300 micromol/l to define the T2T-ULT arm and we will compare
   it with not achieving a SU target of ≤360 micromol/l,
- 225 We will further censor the follow-up when people will discontinue ULT,
- We will exclude from the FAF-ULT arm, those patients who will not have measured serum urate
   levels within 12 months after ULT initiation.
- 228 Also, we will stratify the analyses using the following prognostic factors:
- 229 Age (>65 and ≤65 years),
- 230 Gender (male and female).
- 231 Feasibility count and sample size considerations
- 232 In a previous study, we identified 96,000 patients with incident gout in CPRD. Of them, 48%

233 (~46,000) were ever prescribed ULT, and 28% (~12,000) and 16% (~7,000) achieved serum urate

- targets of  $\leq$ 360 micromol/l and  $\leq$ 300 micromol/l within 1 year after the first ULT prescription, respectively [2].
- 236 Approximately, 20,000 patients with an incident diagnosis of gout were ascertained in VEGA. Of
- them, 42% (~8,000) were prescribed ULT [30]. We assume a similar rate of success as in CPRD. Thus,
- data for approximately 14,000 exposed and 30,000 unexposed patients and 8,000 exposed and
- 239 30,000 unexposed patients will be available for the main aim and the secondary aim, respectively.
- Based on these data, our study will have more than 99% power to detect a risk difference of 1/1,000
- person-years assuming a rate of MACE of 17/1,000 person-years [5] in the unexposed and an alphaerror of 0.025.
- 243 Ethics, funding, and patient partner in research involvement

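### The protocol's inputs give about 30–40% power for a difference of 1/1,000 person-years, not more than 99%

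*Protocol*

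**What the plan says.** All the inputs stand in the protocol.

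- **Power claim** (Feasibility count and sample size considerations): "our study will have more than 99% power to detect a risk difference of 1/1,000" person-years. The comparator rate is given as "person-years assuming a rate of MACE of 17/1,000 person-years [5] in the unexposed", and alpha as 0.025 without a statement of sidedness.
- **Numbers** (same section): "data for approximately 14,000 exposed and 30,000 unexposed patients and 8,000 exposed and" "30,000 unexposed patients will be available for the main aim and the secondary aim, respectively".
- **Source of the numbers** (same section): about 46,000 patients prescribed urate-lowering therapy (ULT) in CPRD, of whom "were ever prescribed ULT, and 28% (~12,000) and 16% (~7,000) achieved serum urate" targets of ≤360 and ≤300 micromol/l within a year. About 8,000 were prescribed ULT in VEGA, with a similar success rate assumed.
- **Time horizon** (Outcomes; Follow up): the primary outcome is the first MACE within 5 years of ULT initiation. Follow-up stops at 5 years or earlier, at transfer out, death, study end or last consultation.
- **Reporting** (Statistical analysis): "The 95% confidence intervals for the difference in 5-year survival" and for the difference in restricted mean survival time come from a bootstrap.

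The section gives no formula, no mean follow-up and no total of person-years.

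**The concern.** A difference of 1/1,000 person-years on a base of 17/1,000 is a relative reduction of about 6%. Accumulated over 5 years at constant rates, it is a risk of 8.15% against 7.69%, or 0.46 percentage points. Detecting so small a difference almost without fail takes far more events than 44,000 patients followed for at most 5 years can supply.

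This sentence is the protocol's only statement of how informative the study will be. The Background criticises earlier trials as too small for cardiovascular outcomes, so a reader will take the figure as assurance that this study does not share the weakness at 1/1,000 person-years. If the figure is wrong, that assurance is unfounded.

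**Working it through.** **Inputs.** Exposed n1 = 14,000; unexposed n0 = 30,000; r0 = 0.017 and r1 = 0.017 − 0.001 = 0.016 per person-year; alpha = 0.025. Follow-up T = 5 years for everyone, the most the protocol allows.

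**Attempt to reproduce the stated figure.** Person-years are 14,000 × 5 = 70,000 and 30,000 × 5 = 150,000. For a difference of two Poisson rates:

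- SE = sqrt(r1/PY1 + r0/PY0) = sqrt(0.016/70,000 + 0.017/150,000) = 0.000585, i.e. 0.585 per 1,000 person-years.
- Expected z = 0.001/0.000585 = 1.71.
- Power, one-sided 0.025: Φ(1.71 − 1.960) = 0.40.
- Power, two-sided 0.025: Φ(1.71 − 2.241) = 0.30.

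The stated figure of more than 99% is not reproduced.

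**Other methods, same inputs, 5 full years.**

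| Method | One-sided 0.025 | Two-sided 0.025 |
|---|---|---|
| Two rates (above) | 40.1% | 29.8% |
| Two proportions, exponential 5-year risks | 38.0% | 27.8% |
| Two proportions, linear risks (8.5% vs 8.0%) | 42.3% | 31.6% |
| Schoenfeld, about 3,521 events, hazard ratio 16/17 | 38.8% | 28.6% |
| Simulated Poisson counts, 200,000 draws | 40.5% | 30.3% |

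**Other inputs, two-rate formula.**

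| Variant | One-sided 0.025 | Two-sided 0.025 |
|---|---|---|
| Secondary comparison, 8,000 vs 30,000, 5 years | 28.6% | 19.9% |
| Mean follow-up 4 years (assumption) | 33.3% | 23.8% |
| Mean follow-up 3 years (assumption) | 26.3% | 18.0% |
| 40,000 unexposed, 5 years | 43.1% | 32.4% |
| 44,000 in each arm, clones treated as independent, 5 years | 73.3% | 63.3% |
| 54,000 in each arm, clones treated as independent, 5 years | 81.6% | 73.2% |
| Stated arms, 14 years (breaks the 5-year cap) | 81.6% | 73.2% |

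Relaxing alpha to one-sided 0.05 gives 52.6% for the main comparison. Among the variants run at 1/1,000 person-years, 99% was reached only by counting every patient in both arms and following all of them for 14 years (one-sided: 99.1% with 44,000 per arm, 99.8% with 54,000). That contradicts both the stated arm sizes and the 5-year cap.

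**Detectable difference.** Solving d/SE(d) = z(alpha) + z(power) with r1 = 0.017 − d, the stated arms and 5 full years:

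- 80% power: d = 1.62/1,000 (one-sided) or 1.77/1,000 (two-sided).
- 99% power: d = 2.43/1,000 (one-sided) or 2.58/1,000 (two-sided).

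At 1/1,000 and a 14:30 split, 99% power needs about 1.38 million (one-sided) or 1.57 million (two-sided) person-years. At most 70,000 + 150,000 = 220,000 are available, so the shortfall is a factor of 6 to 7.

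**Counts.** Initiators: 46,000 + 8,000 = 54,000. Patients in the power statement: 14,000 + 30,000 = 44,000. Subtracting 14,000 exposed from 54,000 leaves 40,000, and the section does not say what happened to the other 10,000.

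**The case against.** The arithmetic itself has no good defence. What can fairly be said on the other side limits how far the point reaches.

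- **The effect size may be the misprint, not the power.** With the same inputs, a difference of 2.5/1,000 gives 99.3% one-sided (98.5% two-sided). This stands: the sentence is wrong as a whole, and the document does not show which element was meant. The fix therefore offers either route.
- **Alpha.** A reader might see a conflict between 0.025 and "The 95% confidence intervals for the difference in 5-year survival". There is none: one-sided 0.025 is the counterpart of a 95% interval, and the study is described as a superiority emulation. Only the sidedness is unstated.
- **Calling 40% a ceiling.** A reader might infer that weighting and the shared first year can only lower the figure. Weighting usually adds variance. But clones shared between arms make the two estimates positively correlated, which reduces the variance of their difference. As an illustration, if first-year variance cancels fully and the 5-year average difference stays at 1/1,000, one-sided power is about 48%; if the effect arises only in years 2–5, it is about 33%. The net direction is not settled by the protocol, and neither case is near 99%.
- **The missing 10,000.** The eligibility rule on urate before ULT and the data windows (2007–2021 and 2007–2017) could remove patients, because the 54,000 come from earlier studies. So 40,000 unexposed is not established. The unexplained drop remains.
- **Attainment.** The Background says "However, only a suboptimal proportion (around 40%) of patients with gout who start ULT will" reach target within 12 months, against 28% in the feasibility section, both citing the same study. A reader might count this against the power figure, but the power statement uses the arm sizes, and the two percentages may have different denominators.
- **Little hangs on it operationally.** The databases are fixed and no recruitment target rests on the figure. This is true, and is why correction costs so little.

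**Conclusion.** The claim of more than 99% power at 1/1,000 person-years does not follow from the inputs given beside it. Those inputs give about 40% (one-sided 0.025, the reading that matches the 95% interval) or 30% (two-sided 0.025) for the main comparison, and about 29% or 20% for the secondary one. This rests on a simple two-rate comparison with 5 full years for every patient, and it ignores weighting and clone correlation. With an assumed mean follow-up of 3–4 years, the main figure is 26–33% one-sided or 18–24% two-sided. Using 40,000 unexposed instead of 30,000 raises the 5-year figure only to 43% or 32%. The gap is too large for rounding or choice of test to explain.

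A reader might go further and conclude that a null result could not exclude a difference of 1/1,000. The documents do not support that: the reported confidence interval will decide it, and the protocol nowhere says a non-significant result will be read as showing no effect. The defect is in the stated power, not in the planned analysis.

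**What to change.** In Feasibility count and sample size considerations:

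1. Replace the statement of more than 99% power. Either give the recomputed power at 1/1,000 person-years (about 40% one-sided or 30% two-sided with 5 full years; about 29% or 20% for the secondary comparison), or give the detectable difference (about 1.6–1.8/1,000 at 80% power, 2.4–2.6/1,000 at 99%).
2. State whether alpha of 0.025 is one-sided or two-sided, and state the assumed mean follow-up or total person-years per arm.
3. Say that the figure comes from a simple two-group comparison and does not account for weighting or for the correlation between clones.
4. Explain how about 54,000 initiators become 14,000 + 30,000, or correct the count and recompute.

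The cost is wording and one short calculation. No data, patients or analyses change. The drawback is that the stated power becomes much less favourable.
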